1.0 PROTOCOL REVISION HISTORY

Protocol Revision Number	Protocol Revision Date
A	13 September 2019
B	25 November 2019

3.3 CLINICAL SITES

The study will be conducted in the following European countries: Austria, Germany, Italy, Poland, Switzerland and United Kingdom. The Sponsor will maintain a list of principal investigators and investigational sites for the duration of the study; the definitive list of sites will be provided with the final clinical investigation report of the study.

4.0 PROTOCOL SYNOPSIS

Title:	ASsessment of the safety and performance of the HARPOON™ Beating Heart Mitral Valve Repair System; a multicenter post-market study (ASCEND)
Protocol Number:	2018-22
Sponsor	HARPOON Medical, an indirect wholly-owned subsidiary of Edwards Lifesciences Corporation
Design:	A single arm, prospective, multicentre, non-randomised and open-label post-market study
Device:	HARPOON™ Beating Heart Mitral Valve Repair System (MVRS)
Population:	Patients with severe degenerative mitral regurgitation as a result of mid-segment posterior leaflet prolapse undergoing treatment with HARPOON™ Beating Heart Mitral Valve Repair System
Enrolment:	250 implanted subjects in up to 25 centers in Europe
Duration:	Initial enrolment: Q4 2019 Last enrolment: Q4 2021 Last follow-up visit: Q1 2027
Follow-up:	Follow-up at 7 days or discharge from hospital post-index procedure (whichever occurs first), at 30 days, and at 6, 12, 18, 24, 36, 48, and 60 months post-treatment
Objectives:	To evaluate the long-term safety and performance of the HARPOON™ MVRS for use in patients presenting with severe degenerative mitral regurgitation due to posterior leaflet prolapse in the post-market phase.
Endpoints:	Primary Safety Endpoint: 
➤ Freedom from all-cause mortality, disabling stroke and life-threatening bleeding at 30 days post-implant. Primary Performance Endpoint: 
➤ Procedure success at 30 days post-treatment, as measured by: Technical success with reduction of MR to less than or equal to mild and the absence of major device or procedure-related SAEs.
Other Planned Analyses:	
➤ Technical success defined as survival and exit from the operating room (OR) with successful implantation of 3 or more expanded polytetrafluoroethylene (ePTFE) chords.➤ Freedom from major device or procedure-related serious adverse event (SAE) at 30 days, 1 year and 2 years post-implant➤ Quality of Life (change from baseline to 1 and 6 months)

- 6-minute walk test (change from baseline to 1 and 6 months)
- Freedom from ePTFE chord rupture as reported by echo core lab at 1 year and 2 years post-implant
- Freedom from reoperation or re-intervention due to ePTFE chord rupture at 1 year and 2 years post-implant
- Functional improvement from baseline NYHA Functional Classification at 1 year and 2 years post-implant
- Freedom from reoperation or reintervention on the mitral valve annually through 5 years post-implant
- Freedom from \geq moderate MR annually through 5 years post-implant

Subject Enrolment:

Inclusion Criteria:

Each subject is required to meet all of the following inclusion criteria:

1. Subject is \geq 18 years old
2. Presence of severe MR as read on a transthoracic echocardiographic study
3. Mitral leaflet coaptation surface is sufficient to reduce mitral regurgitation without undue leaflet tension (approximate leaflet to gap ratio of 2:1) based on the judgment of the patient eligibility committee and the operating surgeon
4. Degenerative mitral valve disease with mid-segment P2 prolapse
5. Patient is able to sign informed consent and able to return for follow-up and is capable of participating in all testing associated with this clinical investigation

Exclusion Criteria:

A subject meeting any of the following criteria shall be excluded:

1. Patient is of the age where further growth is expected
2. Active endocarditis
3. Left ventricular or left atrial appendage thrombus
4. Severe mitral annular and/or leaflet calcification
5. Cannot tolerate procedural anticoagulation or post-procedure antiplatelet regimen
6. Mitral stenosis
7. Functional Mitral Valve disease
8. Previous mitral valve replacement surgery
9. Fragile or thinning apex
10. Contraindications to transoesophageal echocardiography (atlantoaxial disease, severe generalized cervical arthritis, upper gastrointestinal bleeding, significant dysphagia and odynophagia, has received extensive radiation to the mediastinum)
11. Patient is pregnant or lactating

Statistical Analysis: The primary safety and performance endpoints will be summarized by counts, percentages and corresponding 95% confidence intervals. Other categorical variables will be summarized by counts and percentages. Continuous variables

will be summarized using means, medians, ranges and standard deviations.

Statistical calculations will be based on all available data. No missing value imputations are planned for primary safety and effectiveness endpoints. Missing month and days for adverse events will be imputed. An initial analysis of apparent product failure will be conducted once 50 patients achieve 12 months of follow-up. Thereafter, a failure analysis will be repeated for each subsequent 10 patients achieving 12 months of follow-up. The rates of apparent product failure will be deemed unacceptable if the lower limit of any 95% confidence interval at 12 months is above 6%.

Study Oversight:

Echo Core Lab will evaluate all echocardiograms performed per protocol. (Echocardiograms will be obtained at Baseline, Discharge, 30 days, 6, 12, 18, 24, 36, 48 and 60 months).

Clinical Events Committee will adjudicate all potential safety endpoints (death, stroke, bleeding) and reintervention post-index procedure through the 2-year follow up.

Safety Review will be conducted for all adverse events reported during the course of the study.

Routine Monitoring will be conducted for reported data per the monitoring plan.

6.0 INTRODUCTION AND BACKGROUND

6.1 MITRAL REGURGITATION, TRANS-APICAL VALVE REPAIR, AND THE HARPOON™ MVRs

Mitral valve disease is the second most common valvular heart disorder requiring surgery in Europe, with nearly 8 million Europeans estimated to have severe mitral valve regurgitation (MR) (AGENAS, 2015). MR results in a volume overload on the left ventricle which in turn leads to ventricular dilation, decreased ejection performance, pulmonary hypertension, symptomatic congestive heart failure, atrial fibrillation, right ventricular dysfunction and death. Successful surgical mitral valve repair restores mitral valve function, eliminates volume overload on the left ventricle, improves symptom status and prevents adverse left ventricular remodelling.

The large majority of MR results from either degenerative disease (caused by elongated or ruptured native chords that fail to support the mitral valve leaflets) or functional ischemic or idiopathic MR (the motion of the normal mitral valve leaflets is restricted by the enlarged ventricle) both of which lead to ineffective valve closure and regurgitation. Other less common causes of chronic primary MR include infective endocarditis, connective tissue disorders, rheumatic heart disease, cleft mitral valve, and radiation heart disease. If the subsequent volume overload of chronic primary MR is prolonged and severe, it causes myocardial damage, heart failure (HF), and eventual death. Correction of the MR is curative (Nishimura *et al.*, 2014).

There is no effective medical treatment for degenerative MR (DMR). Medical treatment, e.g. diuretics, vasodilators, might relieve HF symptoms but does not alter the course of DMR and ultimately surgery will be required (Nishimura *et al.*, 2016). Two-thirds of all mitral valve surgical procedures in North America are performed on patients with degenerative MR and that percentage is estimated to be similar in Europe. Open cardiac surgery is a common method of treating DMR which involves replacing and/or supplementing elongated or ruptured chords with artificial chords made of ePTFE, a commercially available material which has a 20+ year history of safety in conventional mitral valve repair procedures.

Current ESC/EACTS Guidelines state that surgery is indicated in:

- asymptomatic patients with LVEF \leq 60% or LVESD \geq 45mm, new onset AF or SPAP $>$ 50mmHg and who are at low surgical risk;
- symptomatic MR patients with LVEF $>$ 30% or those who are refractory to medical treatment and in whom a durable valve repair is likely with low comorbidity.

In all patients, valve repair rather than valve replacement is advocated whenever possible and is now the standard of care (Vahanian *et al.* 2012). A systematic review found that mortality is particularly high in patients $>$ 80 years old: 10% for MV replacement (N=3,105) compared with 7% for MV repair (N=2,642), with 5-year survival rates of 23% for MV replacement (N=335) and 29% for MV repair (N=250). It was concluded that many patients are unfit for major heart surgery (Andalib *et al.* 2014).

Although open-heart surgery is the gold-standard approach for the treatment of severe MR, it is not performed in up to 50% of patients due to the increased risk associated with co-morbidities. Excellent outcomes can be achieved in most patients with minimally invasive approaches and transcatheter mitral interventions might be an alternative therapeutic option (Maisano *et al.* 2015; Lam *et al.* 2011).

Mitral valve repair technologies, including the HARPOON™ Beating Heart MVRS (Chordal repair), can be used in cases of DMR. The following available treatments to replace ruptured or elongated chordae tendinae can reduce MR. However, other than the HARPOON™ Beating Heart Mitral Valve Repair System, there is no currently effective medical therapy that treats or cures MR.

- **Edge-to-edge leaflet repair:** MitraClip (Abbott Vascular); Cardica Mitral Repair (Cardica); MitraFlex (TransCardiac); PASCAL (Edwards Lifesciences)
- **Chordal repair:** ePTFE sutures, HARPOON™ MVRS (HARPOON Medical), NeoChord DS1000 (NeoChord); V-Chordal-Off Pump (Valtech); V-Chordal-Transfemoral (Valtech); MISTRAL (Mitralix)
- **Indirect annuloplasty:** CARILLON (Cardiac Dimensions) (Lam *et al.* 2011).
- **Direct annuloplasty:** GDS Accucinch (GDS); Mitralign Bident (Mitralign); Cardioband TF (Valtech); Millipede Ring (Millipede); Kardium MR (Kardium); ValCare MV Repair (ValCare), QuantumCor (QuantumCor)
- **Enhanced coaptation:** Mitra-Spacer-Transapical (Cardiosolutions) (Maisano *et al.* 2015), Middle Peak Medical, US

6.2 DEVICE DESCRIPTION

The HARPOON™ Beating Heart Mitral Valve Repair System, known hereafter as HARPOON System, is described in detail in the Instructions For Use (IFU). The IFU will be provided to the sites and Ethics Committees (ECs), and a copy is part of the Trial Master File and Investigator Site File.

6.2.1 REGULATORY STATUS

The HARPOON System is CE-marked. Its use in this study is consistent with the product's labelling.

6.2.2 INDICATION FOR USE

The HARPOON System is indicated to reduce the degree of mitral regurgitation in patients with severe MR caused by mid-segment posterior leaflet prolapse as a result of degenerative mitral valve disease by delivering and anchoring ePTFE chords to the prolapsed mitral valve leaflet in a beating heart.

6.2.3 TECHNICAL DESCRIPTION OF THE DEVICE

The HARPOON System consists of two parts: 1) HARPOON Introducer and 2) HARPOON Delivery System. Both items are essential for proper delivery of ePTFE implants in the mitral valve leaflet to eliminate or reduce mitral valve regurgitation (MR). The HARPOON System is a Class III product following rule 8 of the Annex IX of the MDD 93/42/EEC (intended to be used to deliver an implant in direct contact with the heart). For a detailed description of the HARPOON System, please refer to the HARPOON™ Beating Heart Mitral Valve Repair System Instructions for Use.

6.2.4 MANUFACTURE OF HARPOON INTRODUCER AND DELIVERY SYSTEM

The HARPOON System (Introducer and Delivery System) are manufactured by HARPOON Medical, an indirect wholly-owned subsidiary of Edwards Lifesciences Corporation.

6.2.5 HARPOON SYSTEM DEVICE DELIVERY AND USE

Please refer to the HARPOON™ Beating Heart Mitral Valve Repair System Instructions for Use for details of the system components and detailed procedure guidelines and instructions.

6.3 PRIOR CLINICAL EXPERIENCE WITH THE HARPOON SYSTEM: EFS AND CE MARK TRIALS

6.3.1 TRIAL INFORMATION

Two (2) ongoing European clinical trials have assessed the safety and performance of the HARPOON System: the Early Feasibility Study (EFS) and the CE Marking Trial (CE Mark, conducted under two (2) clinical protocols):

Clinical Investigation Plan (CIP) Title		CIP Number(s)
EFS	Safety and Performance Study of the Harpoon Medical Transapical Suturing Device (TSD-5) in Subjects with Degenerative Mitral Regurgitation – Early Feasibility Study	HMFIM -1000-PL
CE Mark	Safety and Performance Study of the Harpoon Medical Transapical Suturing Device (TSD-5) in Subjects with Degenerative Mitral Regurgitation – CE Marking for the Harpoon Medical Device	HMFIM -1000-PL-02 and HMCE-1002-00

6.3.2 OBJECTIVES AND DESIGNS

The purpose of the EFS trial is to assess the safety and performance of the HARPOON System (previously the Harpoon Medical TSD-5 Device). The early data collected from the trial were used to power and support the design of the study to support CE Mark of the HARPOON System. The EFS is an open-label, prospective, non-randomized, multicenter European single-arm early feasibility study to demonstrate the performance and safety of the HARPOON System in subjects with degenerative mitral regurgitation. After implantation of the study device, subjects are followed at 30 days, 6 months, and annually for 3 years post-procedure.

The purpose of the CE Marking trial is to assess the safety and performance of the HARPOON System in subjects with severe degenerative mitral regurgitation by implanting ePTFE chords in the posterior leaflet of the mitral valve using a transcatheter approach via transapical access thereby obviating the need for open surgery and its risks. The CE Marking trial is an open-label, prospective, non-randomized, multicenter observational trial without concurrent or matched controls. Following a pre-surgical assessment, subjects are followed for 30 days to demonstrate that the study device performs as designed and has the ability to successfully implant one or more ePTFE chords on the mitral valve via a small left thoracotomy on the beating heart and reduce mitral regurgitation from severe to \leq moderate at the conclusion of the procedure and at 30 days post-procedure. Subjects will be followed thereafter at 6 month intervals for a minimum of three (3) years post-surgical experience.

6.3.3 ENROLMENT AND FOLLOW-UP

This clinical experience summary is based on clinical data as of 02 April 2019 for subjects enrolled from 16 February 2015 (first enrolment in EFS) to 07 November 2017 (last enrolment in CE Mark).

Sixty-five (65) subjects were enrolled at six (6) investigational sites between both studies. This includes thirteen (13) subjects enrolled in the EFS study and fifty-two (52) subjects in the CE Mark study. Of the

CONFIDENTIAL AND PROPRIETARY DATA: THIS DOCUMENT AND THE INFORMATION CONTAINED HEREIN MAY NOT BE REPRODUCED, USED, OR DISCLOSED WITHOUT WRITTEN PERMISSION FROM EDWARDS LIFESCIENCES LLC

enrolled population, sixty-two (62) subjects were implanted with the HARPOON System (thirteen (13) in the EFS trial and forty-nine (49) in the CE Mark Trial). Three subjects left the operating room without the investigational device. One case was aborted before the Harpoon procedure and 2 cases were converted to SOC mitral valve surgery.

Overall, follow-up compliance of 100% (56/56) of eligible subjects was achieved at the 1-year visit. Six (6) HARPOON System subjects were censored through 1-year including two (2) deaths and four (4) reoperations. Follow-up compliance of 98% (40/41) has been achieved so far at the 2-year visit; nine (9) subjects have yet to reach their 2-year follow-up window. Follow-up is currently ongoing.

6.3.4 SAFETY ENDPOINTS

Table 1 summarizes the early (≤ 30 POD) and late (>30 POD) complication rates for the trial safety endpoints for the implanted (HARPOON System) cohort. Early event rates are described as simple proportions; late event rates utilize linearized (person-year) rates.

Table 1: Prior Clinical Experience: Safety endpoints for the implanted cohort

Endpoint	Early (≤ 30 POD) N = 62 n,m (%/N)	Late (>30 POD) LPY = 99.0 n,m (%/pt-yr)
Mortality	1, 1 (1.6)	2, 2 (2.0)
Study Device Reoperation	1, 1 (1.6)	10, 10 (10.1)
Thromboembolism	0, 0 (0.0)	1, 1 (1.0)
Stroke	0, 0 (0.0)	0, 0 (0.0)
TIA	0, 0 (0.0)	0, 0 (0.0)
Non-cerebral Embolism	0, 0 (0.0)	0, 0 (0.0)
Endocarditis	1, 1 (1.6)	0, 0 (0.0)
Myocardial Infarction	3, 3 (4.8)	0, 0 (0.0)
Renal Failure	0, 0 (0.0)	0, 0 (0.0)

'n' is the number of subjects with the event; 'm' is the number of events; LPY: late pt-yrs.

Early rates are reported as n/N; late linearized rates are reported as m/LPY

One (1) early (1.6%) and two (2) late (2.0%/pt-yr) deaths have been reported. The CEC has adjudicated one (1) early death with primary cause of death cardiac arrest, and not related to the study device. One of the two (2) late deaths was adjudicated as caused by aortic dissection and device related, and the second late death was a sudden death with unknown causality, and therefore was also counted as device related.

One (1) early (1.6%) and ten (10) late (10.1 %/pt-yr) reoperations have been reported, including nine (9) repairs and two (2) mitral valve replacements. See Section 6.3.6.1 for more information on reoperations that have occurred. There were no reports of unanticipated adverse device effects.

6.3.5 PRIMARY PERFORMANCE RESULTS

In the EFS study, procedural success was defined as the subject leaving the operating room with at least one (1) ePTFE chord in place, having a Discharge MR grade of \leq mild and 30 Day MR grade \leq mild,

without a reoperation prior to 30 days. Procedural success was achieved in 84.6% (11/13) of the ENROLLED cohort.

In the CE Mark study, Procedural success was defined as the subject leaving the operating room with at least one (1) ePTFE chord in place, having a Discharge MR grade of \leq Moderate and 30-Day MR grade \leq Moderate, without a reoperation prior to 30 days. Procedural success was achieved in 88.5% (46/52) of the ENROLLED cohort.

6.3.6 SECONDARY PERFORMANCE RESULTS

6.3.6.1 MITRAL REGURGITATION

Table 2 presents the mitral regurgitation (MR) severities as evaluated by the Echo Core Lab at the baseline, discharge, 1-month, 6-month, 1-year, and 2-year follow-up visits for the HARPOON System cohort.

Several subjects with moderate to severe mitral regurgitation underwent re-operations and were identified as having ruptured ePTFE chords. An investigation was conducted to determine the root cause of ePTFE chord ruptures. The root cause of the chord ruptures was found to be over-tensioned chords. Findings confirmed that no material or device design changes were required. As a result of this investigation, screening and procedural updates to the IFU, Training Program Materials, and Post-Market Clinical Follow-up Study were made to mitigate future ePTFE chord ruptures.

Table 2: Prior Clinical Experience: Mitral Regurgitation Results

Visit	Severity	% (n/N)	Visit	Severity	% (n/N)
Baseline	None	0.0% (0 /57)	6 Month Follow-up	None	17.2% (10 /58)
	Trace	0.0% (0 /57)		Trace	34.5% (20 /58)
	Mild	0.0% (0 /57)		Mild	29.3% (17 /58)
	Moderate	7.0% (4 /57)		Moderate	10.3% (6 /58)
	Severe	93.0% (53 /57)		Severe	8.6% (5 /58)
Discharge	None	22.4% (13 /58)	1 Year Follow-up	None	9.6% (5 /52)
	Trace	51.7% (30 /58)		Trace	42.3% (22 /52)
	Mild	20.7% (12 /58)		Mild	23.1% (12 /52)
	Moderate	3.4% (2 /58)		Moderate	23.1% (12 /52)
	Severe	1.7% (1 /58)		Severe	1.9% (1 /52)
1 Month Follow-up	None	11.7% (7 /60)	2 Year Follow-up	None	2.6% (1 /38)
	Trace	50.0% (30 /60)		Trace	47.4% (18 /38)
	Mild	23.3% (14 /60)		Mild	15.8% (6 /38)
	Moderate	13.3% (8 /60)		Moderate	26.3% (10 /38)
	Severe	1.7% (1 /60)		Severe	7.9% (3 /38)

N represents the number of subjects with evaluable data at the specified visit.

If a subject has multiple assessments in the same visit window, the worst severity is summarized.

6.3.6.2 NYHA FUNCTIONAL CLASS

Performance was also assessed using NYHA functional classification change. At 1 year of follow-up, 92.3% of subjects were in NYHA class I, 5.8% were in NYHA class II, and 1.9% were in NYHA class III, corresponding to an improvement (50%) or maintenance (48%) of NYHA class for 98% (51/52) of subjects.

6.3.7 SUMMARY

The results of the EFS and CE Marking trials support the safety and performance of the HARPOON System.

7.0 STUDY DESIGN

7.1 OBJECTIVE

The objective of this study is to evaluate the long-term safety and performance of the HARPOON System for use in patients presenting with severe degenerative mitral regurgitation due to posterior leaflet prolapse in the post-market phase.

7.2 DESIGN

A single arm, prospective, multicentre, non-randomised and open-label, post-market study.

7.3 ENDPOINTS

The following are the planned endpoints for the study:

7.3.1 PRIMARY SAFETY ENDPOINT:

- Freedom from all-cause mortality, disabling stroke and life-threatening bleeding at 30 days post-implant.

7.3.2 PRIMARY PERFORMANCE ENDPOINT:

- Procedure success at 30 days post-treatment, as measured by: technical success with reduction of MR to less than or equal to mild and the absence of major device or procedure-related SAEs.

7.3.3 OTHER PLANNED ANALYSES:

- Technical success defined as survival and exit from the operating room (OR) with successful implantation of 3 or more expanded polytetrafluoroethylene (ePTFE) chords
- Freedom from major device or procedure-related serious adverse event (SAE) at 30 days, 1 year and 2 years post-implant
- Quality of Life (change from baseline to 1 and 6 months)
- 6-minute walk test (change from baseline to 1 and 6 months)
- Freedom from ePTFE chord rupture as reported by echo core lab at 1 year and 2 years post-implant
- Freedom from reoperation or re-intervention due to ePTFE chord rupture at 1 year and 2 years post-implant
- Functional improvement from baseline NYHA Functional Classification at 1 year and 2 years post-implant
- Freedom from reoperation or reintervention on the mitral valve annually through 5 years post-implant
- Freedom from \geq moderate MR annually through 5 years post-implant

7.3.4 KEY ENDPOINT DEFINITIONS:

A complete list of definitions can be found in **Attachment A**. Key endpoint definitions include:

All-cause mortality:

Mortality for any cause will be reported with a further stratification by Cardiovascular and Non-Cardiovascular. All Deaths will be adjudicated for a cause of death and relationship to the investigational device and the index/implant procedure.

Cardiovascular mortality

Expirations for any of the contributing conditions such as Heart failure, Myocardial infarction, Major bleeding, Thromboembolism, Stroke, Arrhythmia and conduction system disturbance, Cardiovascular infection and sepsis (e.g., mediastinitis and endocarditis), Tamponade, Sudden, unexpected death Other cardiovascular, Device failure, Death of unknown cause (adjudicated as cardiovascular)

Noncardiovascular mortality

Any death in which the primary cause of death is clearly related to another condition such as Non-cardiovascular infection and sepsis (e.g., pneumonia,) Renal failure, Liver failure, Cancer, Trauma, Homicide, Suicide, Other non-cardiovascular causes.

Disabling Stroke

Stroke is defined as a focal or global neurological deficit lasting more than 24 h OR less than 24 h if available neuroimaging documents a new intracranial or subarachnoid hemorrhage (hemorrhagic stroke) or central nervous system infarction (ischemic stroke) OR the neurological deficit results in death.

A disabling stroke includes any neurological deficit (for example partial visual field cut) with a modified Rankin scale score equal or more than 2 with an increase in equal 1 or more modified Rankin scale score category from individual's pre-stroke baseline at 90 days after stroke onset.

Life-threatening Bleeding

Bleeding in a critical organ, such as intracranial, intraspinal, intraocular, intrathoracic, or pericardial necessitating surgery or intervention, or intra- muscular with compartment syndrome *OR* bleeding causing hypovolemic shock or hypotension (systolic blood pressure <90 mm Hg lasting >30 min and not responding to volume resuscitation) or requiring significant doses of vasopressors or surgery.

Fatal Bleeding: Bleeding adjudicated as being a proximate cause of death. Severe bleeding adjudicated as being a major contributing cause of a subsequent fatal complication, such as MI or cardiac arrest, is also considered fatal bleeding.

Major device or procedure related serious adverse event

All Major Serious Adverse Events adjudicated as device or procedure related, as defined by modified MVARC (Stone, et al.) including:

- Procedure or Device related Death
- Procedure or Device related Stroke
- Procedure or Device related Life-threatening bleeding (MVARC scale)
- Major vascular or access (index procedure) complications
- Major cardiac structural complications related or cause by device or procedure
- Procedure related Stage 2 or 3 acute kidney injury (includes new dialysis)
- Procedure related Myocardial infarction or coronary ischemia requiring PCI or CABG
- Procedure or device related severe hypotension, heart failure, or respiratory failure requiring intravenous pressors or invasive or mechanical heart failure, treatments such as ultrafiltration or hemodynamic assist devices, including intra-aortic balloon pumps or left ventricular or biventricular assist devices, or prolonged intubation for more than 48 h.
- Any device-related dysfunction, migration, thrombosis, or other complication requiring surgery or repeat intervention including:
 - Structural or Functional failure of the HARPOON device, introducer or artificial chords (ePTFE) requiring an intervention.
 - Conversion to the Open Mitral Valve Surgery secondary to mitral valve apparatus damage or dysfunction, requiring surgical valve repair or replacement, or Secondary to procedural complications (such as cardiac perforation, removal of an embolized artificial chords, injury to Aortic valve and so on)
 - Device malpositioning (Artificial chords malpositioning) requiring intervention. Permanent deployment of **artificial chord(s)** in a location other than intended or movement of the artificial chords during or post deployment which requires an intervention.
 - Artificial Chord detachment (used with HARPOON device) which requires an intervention
 - Device fracture: a break, tear, perforation, or other structural defect in the artificial chords (housing, leaflet, and so on) resulting in device failure, resulting in recurrent MR symptoms, or requiring reintervention.
 - Damage to the native mitral valve apparatus (damage to native chordae tendinae, Leaflets, Papillary muscles or Mitral annulus) requiring an intervention or conversion to Open Mitral Valve Surgery.
 - Symptomatic or requiring intervention Device Thrombosis (any thrombus attached or near the artificial HARPOON implanted chords)
 - Interaction with non-mitral valve intracardiac structures which requires intervention and
 - Endocarditis (as diagnosed by modified Duke endocarditis criteria or evidence of abscess, pus, or vegetation confirmed as secondary to infection

by histological or bacteriological studies during an operation or autopsy) which required a surgical intervention.

- Hemolysis (a presence of a leaflet perforation on transesophageal or transthoracic echocardiography plus anemia requiring transfusion plus increased haptoglobin and/or LDH levels; which lead to a surgical intervention.
- Other major device or procedure related SAEs

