9.5.3 PRIMARY FOLLOW-UP ASSESSMENTS

Post-procedure management: Standard hospital protocols for the management of subjects after mitral valve surgery shall be followed.

7-Day/Discharge assessment: All subjects shall be discharged from the hospital at the discretion of the attending cardiac surgeon. Prior to discharge, all subjects shall undergo a comprehensive pre-discharge TTE as well as a physical exam on either day 7 or at the time of discharge, whichever occurs first.

Primary subject follow-up: Subjects shall be seen at 30 days (+20/-0 days) after the HARPOON System procedure. A TTE and specific clinical assessments, in accordance with the Schedule of Assessments, shall be performed at that time.

Additional clinical and TTE follow-up shall occur for all active subjects in accordance with the Schedule of Assessments at the following intervals:

- 6-months (+/- 30 days)
- 12-months (+/- 30 days)
- 18-months (+/- 30 days)
- 24-months (+/- 60 days)
- 36-months (+/- 60 days)
- 48-months (+/- 60 days)
- 60 months (+/- 60 days)

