10.5 STATISTICAL ANALYSIS METHODOLOGY

The primary safety and performance endpoints will be summarized by counts, percentages and corresponding 95% confidence intervals. Other categorical variables will be summarized by counts and percentages. Continuous variables will be summarized using means, medians, ranges and standard deviations. Time to event analysis, including survival probabilities and standard errors, will be estimated using the Kaplan Meier method. Time to event will be calculated in days and standard errors will use the greenwood algorithm.

Statistical calculations will be based on all available data. No missing value imputations are planned for the primary and secondary analyses will be performed. Missing month and days for adverse events will be imputed. Regarding the secondary endpoint, an initial analysis of apparent product failure will be conducted once 50 subjects achieve 12 months of follow-up. Thereafter, a failure analysis will be repeated for each subsequent 10 subjects achieving 12 months of follow-up. The rates of apparent product failure will be deemed unacceptable if the lower limit of any 95% confidence interval at 12 months is above 6%.

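### Procedure success does not require survival to day 30, so an unrelated death after leaving the operating room can drop out of the primary performance rate

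*Combined protocol and SAP*

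**What the plan says.** Sections 4.0, 7.3.2 and 10.3.2 define procedure success at 30 days in the same way: "technical success with reduction of MR to less than or equal to mild and the absence of major device or procedure-related SAEs". Its parts are defined elsewhere in Section 7.3:

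- **Technical success:** "Technical success defined as survival and exit from the operating room (OR) with successful implantation of 3 or more" ePTFE chords. This is the only mention of survival, and it ends at the operating-room door.
- **Major SAEs:** "All Major Serious Adverse Events adjudicated as device or procedure related". The death item on that list reads "Procedure or Device related Death", and the closing catch-all item is likewise confined to related events. Attachment A repeats the list.

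Death from any cause appears only in the primary safety endpoint: "Freedom from all-cause mortality, disabling stroke and life-threatening bleeding at 30 days post-implant".

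On timing, Section 9.5.3 states: "Subjects shall be seen at 30 days (+20/-0 days) after the HARPOON System procedure". The same section also schedules a transthoracic echo before discharge.

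On missing data, Section 10.5 states: "Statistical calculations will be based on all available data". The synopsis rules out imputation for the primary endpoints. Section 10.1, however, sets the analysis population as the 250 implanted subjects whatever the outcome of the procedure.

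**The concern.** Take a subject who leaves the operating room with three chords in place and dies on day 10 of a cause adjudicated unrelated to both device and procedure. None of the three components is failed as written, yet the subject cannot have an echo in the 30-day window. The endpoint does not say how to score this case. If the subject is treated as having no MR grade, the available-data rule removes a dead patient from the main performance figure, and the remaining subjects show a higher success rate. The error can run only in the favourable direction.

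Scoring then depends on a relatedness judgement that is hard to make for a death within 30 days of transapical surgery. The prior experience shows the difficulty: "The CEC has adjudicated one (1) early death with primary cause of death cardiac arrest, and not related to the study device" (Section 6.3.4). Whether that death was related to the procedure is not stated.

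**Working it through.** **Step 1. Apply the definition to a day-10 unrelated death.**

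| Component | Source | Result |
|---|---|---|
| Technical success | 7.3.3 | Met: alive on leaving the operating room, 3 chords |
| MR mild or less at 30 days | 7.3.2, 9.5.3 | No grade: the window runs from day 30 to day 50 (30 + 20) |
| No major related SAE | 7.3.4 | Met: the death was adjudicated unrelated |

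No component is failed and one cannot be observed. Available data without imputation (4.0, 10.5) point to exclusion. The population definition (10.1) points to retention. The plan does not reconcile the two for this case.

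**Step 2. The plan's own figure.** Section 10.2.1 aims for precision of 5% or better at n = 250 for rates from 2% to 17%. The normal-approximation half-width is 1.96 × √(p(1−p)/250):

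- p = 0.02: 1.74 points
- p = 0.17: 4.66 points

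The stated figure reproduces on that basis. With exact limits the longer side at 42/250 is 5.2 points, a marginal miss. Nothing in this point changes the sample-size rationale.

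**Step 3. Inputs for the size of the effect.**

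- Early deaths in the prior studies: 1/62 = 1.6%, exact 95% CI 0.04% to 8.7% (count from Table 1). Scaled to this study: 250/62 = 4.03, or about 4.
- Illustrative success rate among survivors: MR mild or less at 1 month in Table 2, (7 + 30 + 14)/60 = 85%. This is the MR component only, so it is an assumption for the composite.
- Assumption: all d early deaths occur after leaving the operating room and are judged unrelated to both device and procedure. The documents do not establish this for the one prior early death.

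**Step 4. Effect of dropping the deaths.** With S successes, N = 250 and d such deaths:

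S/(N−d) − S/N = [S/(N−d)] × (d/N)

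Each death therefore adds the survivors' success rate times 1/250. At 85% that is 0.85 × 0.4 = 0.34 points, and it cannot exceed 0.4.

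| d | Dropped | Counted as failure | Difference (points) |
|---|---|---|---|
| 1 | 212/249 = 85.1% | 212/250 = 84.8% | 0.34 |
| 4 | 209/246 = 85.0% | 209/250 = 83.6% | 1.36 |
| 8 | 206/242 = 85.1% | 206/250 = 82.4% | 2.72 |
| 22 | 194/228 = 85.1% | 194/250 = 77.6% | 7.49 |

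The last row takes the upper exact limit for 1/62 (0.0866 × 250 = 21.7) and again makes every death unrelated. It marks the edge of the range, not an expectation. For d = 4 the exact 95% intervals are 79.9% to 89.2% (dropped) and 78.4% to 88.0% (failure). With survivor success of 80% or 90%, the d = 4 difference is 197/246 − 197/250 = 1.28 points or 221/246 − 221/250 = 1.44 points.

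**Step 5. Scale.** At 85% and n = 250 the standard error is √(0.85 × 0.15/250) = 2.26 points and the 95% half-width is 1.96 × 2.26 = 4.43 points. The 1.36-point shift is 1.36/4.43 = 0.31 of that half-width.

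**The case against.** The strongest reply is that the plan can already be read as scoring such a subject a non-success. The endpoint is set at 30 days, a subject with no 30-day grade has not shown the MR component, and Section 10.1 keeps every implanted subject. A known death is not a missing value, so calling it a failure needs no imputation. The prior studies reported procedural success over the whole enrolled cohort (11/13 and 46/52, Section 6.3.5). This reading is reasonable, but no section states it. The prior definitions named a 30-day MR grade explicitly, and Section 6.3.5 does not say how the early death was scored.

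The affected group is also narrow, and this stands. Deaths in the operating room already fail technical success. A relation to either device or procedure is enough for failure. Section 11.2 has investigators class unassessable events as possibly related, and a prior late sudden death of unknown cause was counted as device related (Section 6.3.4). The documents identify no confirmed case of an early death unrelated to both.

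It also stands that no decision turns on this. There is no hypothesis test or performance goal, and every 30-day death is reported in the primary safety endpoint. A scoring rule might sit in the pre-specified SAP cited in Section 10.6.4 or in the CEC Charter, but none appears in the text available.

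A reader might go further and infer that the dead subject can count as a success on the strength of a good discharge echo. The documents do not support that: nothing authorises the discharge echo in place of the 30-day one, and the no-imputation rule weighs against carrying it forward. Nor do the two primary endpoints contradict each other by treating the same death differently, since one measures all-cause safety and the other procedural performance.

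**Conclusion.** The gap is real but minor. As written, a death after leaving the operating room and before day 30, judged unrelated to device and procedure, fails no component of procedure success. The available-data rule would most naturally remove it from the denominator, in tension with Section 10.1. The resulting bias is always upward: about 0.34 points per such death at 85% success, and about 1.4 points if all of the roughly 4 early deaths suggested by 1/62 were of this kind. That last condition is an assumption resting on a single prior event whose relation to the procedure is not given, so the realistic effect may well be smaller. The effect is confined to the reported rate and its confidence interval. Power, error rates and the visibility of the deaths are untouched.

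**What to change.** In Sections 4.0, 7.3.2 and 10.3.2, add being alive at 30 days as a component of procedure success. State that any death through day 30 is a failure kept in the denominator, whatever its adjudicated relatedness and whether or not an echo exists. State also that the 30-day transthoracic echo, as read by the core lab, decides the MR component. Report the relatedness of deaths as a descriptive line.

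The cost is one or two sentences in the definition, carried into the analysis specification. Vital status at 30 days is already needed for the primary safety endpoint, so no new data are required. The reported success rate may be slightly lower. The clause does not settle how to handle a subject who is alive at day 30 but has no in-window echo, which remains an ordinary missing-data question.
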